## List of Acronyms

Activated Clotting Time	ACT
Advanced Cardiovascular Life Support	ACLS
Adverse Event	AE
Atrioventricular	AV
Esophageal Cooling Device	ECD
Food and Drug Administration	FDA
Luminal Esophageal Temperature	LET
Principal Investigator	PI
Pulmonary Vein Isolation	PVI
Radiofrequency (Ablation)	RF
Serious Adverse Event	SAE
Transesophageal Echocardiography	TEE
Unanticipated Problem	UP

## 1. Study Summary

Title	Esophageal cooling in radiofrequency cardiac ablation: Pilot study
Protocol Number	RMC IRB # 187
Study Design	Randomized, Single-Blind, Interventional, Post-Market pilot study
Study Duration	1 Year
Sample Size	6
Primary Objective	To assess the reduction in the occurrence and severity of esophageal injury in patients who have the EnsoETM inserted into the esophagus during Radiofrequency (RF) ablation.
Secondary Objectives	To assess the safety of the EnsoETM and efficacy of ablation when the EnsoETM is used to regulate temperature
Exploratory Objectives	To assess the EnsoETM's ease of use during ablation

## 2. Introduction

### 2.1. Background Information

#### 2.1.1. Atrial and Ventricular Arrhythmias

Atrial and ventricular arrhythmias include a broad range of atypical myocardial conduction which are named based on their site of origin. Intervention for these arrhythmias include medications and/or ablation strategies. Of primary interest is the atrial arrhythmia termed atrial fibrillation. This type of arrhythmia involves multiple points of origin typically in the left atrium and the base of the pulmonary veins at the junction of the left atrium. The most common ablative strategy includes pulmonary vein isolation which involves heating (RF ablation) or cooling of the posterior aspect of the left atrium which lies near the esophagus.

#### 2.1.2. EnsoETM Device Description

The EnsoETM is a silicone tube with three lumens that is placed in the esophagus. Distilled water is circulated through the two cooling lumens, while the third lumen connects to wall suction and is used for standard gastric decompression. The EnsoETM is composed of standard medical-grade silicone, and it is a single-use, disposable, non-implantable device with an intended duration of use of 36 hours or less. In 2015, Attune Medical, LLC received approval from the FDA on their *de novo* request for classification of the Esophageal Cooling Devices (ECD) named EnsoETM. This class II device is used to apply a specified temperature to the endoluminal surface of the esophagus via an external controller. This study will be utilizing the EnsoETM, because it is designed to fit the Gaymar Medi-Therm III Conductive Hyper/Hypothermia SystemNaiman. There are three contraindications for this device: (1) patients with known esophageal deformity or evidence of esophageal trauma, (2) patients with known ingestion of acidic or caustic poisons within the prior 24 hours, and (3) patients with less than 40 kg of body mass.Naiman, Shanley

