#### **Limitations:**

Prescription use only: Federal (USA) law restricts this device to sale by or on the order of a physician.

The EnsoETM may cause or exacerbate esophageal tissue damage in patients with esophageal deformity or evidence of esophageal trauma, or in patients who have ingested acidic or caustic poisons within the prior 24 hours.

The safety and effectiveness of the EnsoETM have not been evaluated in patients with less than 40 kg of body mass

The EnsoETM should only be used by healthcare professionals with training in the use of orogastric tubes and the use of the Gaymar Medi-Therm III Conductive Hyper/Hypothermia System.

The EnsoETM is intended for esophageal placement. Inserting the EnsoETM in the trachea, bronchi, or lungs can result in serious harm.

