Attachment of the EnsoETM to unapproved or unintended connections can result in serious patient harm

The presence of the EnsoETM may interfere with other devices in the esophagus or mouth. Dual placement of other devices in the esophagus with the EnsoETM in place, such as an enteral feeding tube, may result in patient harm.

Large patients with body mass greater than 120 kg may exhibit slower responses to intended temperature changes. Small patients with a body mass less than 60 kg may exhibit faster cooling than anticipated, and may exhibit slower rewarming than anticipated.

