### **5.2. Exclusion Criteria**

- Subject has known esophageal deformity, or evidence of esophageal trauma, prior radiation therapy involving the esophagus, or previous esophageal disease (for example, known esophageal varices, cirrhosis, history of esophagectomy, previous swallowing disorders or dysphagia, achalasia, known ingestion of acidic or caustic poisons within the prior 24 hours etc.).
- Subject is incarcerated
- Subject is pregnant or plans to become pregnant
- Subject has a silicone allergy
- Subject has esophageal bleeding prior to EnsoETM insertion

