## 7. Study Procedures and Schedule

### 7.1. Study Procedures/Evaluations

#### 7.1.1. Study Specific Procedures

- Study specific imaging will include endoscopic evaluation of the esophagus one day before surgery at the time of the pre-op Transesophageal Echocardiography (TEE) and again 1-day post-op. This will include endoscopic esophageal intubation with visual assessment of the entire esophagus and grading of lesions. Coupled with this procedure will include endoscopic ultrasound assessment of the esophagus at the level of the left atrium with specific attention to the sub-mucosal layer that separates esophagus from the cardiac tissue. The patient will undergo moderate sedation during this procedure, which will accompany the TEE.
- The ECD will be placed by trained study staff following endotracheal intubation. Proper positioning will be verified. A temperature probe will be placed to verify the patient's core temperature. The target temperature will be set to the core temperature at the beginning of the procedure. Two minutes prior to ablation on the posterior wall the target temperature will be changed to the minimum temperature setting which will allow for maximal cooling. Cooling will take place throughout the duration of posterior wall ablation. After ablation in this territory is complete the target temperature will return to the patient's core temperature. The device will be removed at the completion of the procedure by anesthesiology when there is no further need for an orogastric tube.
- LET monitoring will not be performed in the patients of the intervention group as the ECD is prohibitive. Therefore, ice lavage of the esophagus, as detailed below, will not be performed in this group.

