#### 7.1.2. Standard Care Procedures

- Medical History will be obtained by interview and will involve identification of contraindications to the use of the ECD. This includes a history of esophageal perforation or varices. An allergy to silicone will be assessed.
- The patient's active medication list will be reviewed as is standard protocol for atrial fibrillation ablation, but this is not specific to the study as there are no medications that would impact the use of the ECD.
- All subjects will be on Protonix (40mg; twice daily) immediately following surgery for 30 days and anticoagulation for 3 months following surgery.
- The physical exam will be performed as is customary for the procedure. Study specific exam is included as part of the airway assessment which is performed on a regular basis by anesthesiology. The oropharynx will be assessed prior to placement of the ECD.

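### The exclusion criteria leave out one of the protocol's own three device contraindications, body mass under 40 kg

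*Protocol*

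**What the plan says.** Section 2.1.2 of the protocol states that "There are three contraindications for this device": esophageal deformity or evidence of trauma, recent ingestion of acidic or caustic poisons, and "3) patients with less than 40 kg of body mass". The Limitations under section 2.1.2.1 return to the last of these: "The safety and effectiveness of the EnsoETM have not been evaluated in patients with less than 40 kg of body mass". They add a wider caution for light patients: "Small patients with a body mass less than 60 kg may exhibit faster cooling than anticipated, and may exhibit slower rewarming than anticipated".

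Section 5.2 excludes subjects with esophageal deformity, trauma or other esophageal disease, ending that list with "known ingestion of acidic or caustic poisons within the prior 24 hours etc". It also excludes incarceration, pregnancy, silicone allergy and esophageal bleeding. It gives no body-mass limit.

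Section 7.1.2 says that the medical history will be used to identify contraindications to the device. It illustrates this with "This includes a history of esophageal perforation or varices", followed by silicone allergy.

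In the device arm, section 7.1.1 sets the target, two minutes before posterior-wall ablation, to "the minimum temperature setting which will allow for maximal cooling".

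**The concern.** Eligibility is what keeps contraindicated patients away from a study device. Here the protocol lists three such groups and its eligibility rules exclude only two. No reason is given for leaving out the third, and because the other two were carried over in nearly the same terms, it looks like an oversight.

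Two things are at stake. The first is safety. A very light patient could be allocated to maximal cooling with a device that the protocol says is contraindicated for them, and harmful hypothermia is among the device risks listed in section 2.3.1. Device safety is also a secondary objective, so an adverse event in such a subject would muddy that result.

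The second is the integrity of the randomised comparison. If the problem is noticed only when the device is about to be placed, it will be noticed only in the device arm. The subject would then cross over to ablation without the device or be lost after randomisation, while an equally light control subject would stay in.

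**Working it through.** No sample-size or power figure is involved, so the check is a comparison of sections.

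**Step 1. Carry each contraindication in section 2.1.2 across to the eligibility rules.**

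| Contraindication (2.1.2) | Inclusion (5.1) | Exclusion (5.2) | Removal (5.5) |
|---|---|---|---|
| Esophageal deformity or trauma | not addressed | excluded | stricture or ulceration only |
| Caustic ingestion, prior 24 hours | not addressed | excluded | not addressed |
| Body mass under 40 kg | not addressed | **not addressed** | not addressed |

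Two of the three are carried over. Section 5.1 asks only for age 18 to 90, an arrhythmia needing posterior ablation, consent, and ability to follow the protocol.

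**Step 2. Look for another rule that closes the gap.**

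- Section 7.3.1 (Visit 1) judges eligibility against the inclusion and exclusion criteria, which contain no weight limit. Vital signs and examinations are recorded there, but weight is not named.
- Section 6.5 measures the patient for tube length, not for mass.
- Section 7.1.2 has a general contraindication check, but it is a history interview listed under standard care. Its examples do not include weight, and nothing says that a positive finding makes the patient ineligible.
- The open ending of the list in section 5.2 closes a set of esophageal conditions and cannot reasonably be read to include body mass.

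**Step 3. Consequence.** An adult under 40 kg who meets the other criteria is eligible as written. Section 9.2.1 allocates 1:1, so the chance of allocation to the device is 1/(1 + 1) = 1/2.

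**Step 4. Size if it happens.** Section 1 gives a sample size of 6. With equal arms, each has 6/2 = 3 subjects, so one such subject is 1/3 of an arm.

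**The case against.** The best counter-argument is that section 7.1.2 already tells staff to look for contraindications. Its examples are introduced as inclusions rather than as a complete list, and section 2.1.2 defines body mass as a contraindication, so a careful reader would check weight. That has some force: such a patient may well be caught in practice. But the instruction does not say what follows from a positive finding, and no exclusion criterion exists to act on.

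It can also be said that section 5.2 is silent rather than contradictory. That is fair as a description, since nothing there invites enrolment below 40 kg. The effect is the same, because a patient who breaches no criterion is eligible.

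The safety argument needs limits too. The faster-cooling warning applies below 60 kg, so a 40 kg limit does not remove that caution for patients between 40 and 60 kg. For patients under 40 kg the Limitations report an absence of evaluation, not a demonstrated harm. Maximal cooling is confined to posterior-wall ablation and the two minutes before it. Section 6.5 requires two temperature monitors, discontinuation if they differ by more than 0.5°C, and coolant no colder than 4°C. These safeguards reduce the hazard. They do not make a contraindicated patient suitable.

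Finally, the event is unlikely among six adults. That limits the importance of the point but is no reason to leave the omission in place.

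**Conclusion.** The concern holds. One of the three contraindications stated in section 2.1.2 is missing from the eligibility criteria, and no other section makes it a ground for exclusion. The change should be made, though the omission does not threaten the trial as a whole.

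The likelihood is low and cannot be quantified from the protocol, which gives no weight distribution. The one-third figure is conditional on such a subject being enrolled and assumes that the six subjects divide equally. Crossover or loss after randomisation is an inference about what staff would do on noticing the contraindication late; the protocol does not describe it.

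**What to change.** Add body mass under 40 kg to the exclusion criteria in section 5.2, so that all three contraindications in section 2.1.2 appear there. Name weight among the Visit 1 measurements in section 7.3.1, and apply the limit to every subject before randomisation, so that exclusion cannot depend on the allocated arm. For consistency, add body mass to the contraindications named in section 7.1.2.

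The cost is one line in section 5.2 and one weight entry at a visit where vital signs and examinations are already recorded. The effect on recruitment should be negligible.

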### 2.1.2.1. Regulatory Status

The Food and Drug Administration (FDA) identifies the EnsoETM as:

**Esophageal thermal regulation device.** An esophageal thermal regulation device is a prescription device used to apply a specified temperature to the endoluminal surface of the esophagus via an external controller. This device may incorporate a mechanism for gastric decompression and suctioning. The device is used to regulate patient temperature.

#### **Indications for Use:**

The EnsoETM is a thermal regulating device, intending to:

- Connect to a Gaymar Medi-Therm III Conductive Hyper/Hypothermia System to control patient temperature, and
- Provide gastric decompression and suctioning

#### **Limitations:**

Prescription use only: Federal (USA) law restricts this device to sale by or on the order of a physician.

The EnsoETM may cause or exacerbate esophageal tissue damage in patients with esophageal deformity or evidence of esophageal trauma, or in patients who have ingested acidic or caustic poisons within the prior 24 hours.

The safety and effectiveness of the EnsoETM have not been evaluated in patients with less than 40 kg of body mass

The EnsoETM should only be used by healthcare professionals with training in the use of orogastric tubes and the use of the Gaymar Medi-Therm III Conductive Hyper/Hypothermia System.

The EnsoETM is intended for esophageal placement. Inserting the EnsoETM in the trachea, bronchi, or lungs can result in serious harm.

Attachment of the EnsoETM to unapproved or unintended connections can result in serious patient harm

The presence of the EnsoETM may interfere with other devices in the esophagus or mouth. Dual placement of other devices in the esophagus with the EnsoETM in place, such as an enteral feeding tube, may result in patient harm.

Large patients with body mass greater than 120 kg may exhibit slower responses to intended temperature changes. Small patients with a body mass less than 60 kg may exhibit faster cooling than anticipated, and may exhibit slower rewarming than anticipated.

### 2.1.3. Prior Clinical Studies

The first case of esophageal trauma associated with left atrial posterior wall ablation for atrial fibrillation was reported in 2003 (Lequerica JL B. E., 2008). Since then there have been a myriad of interventions in hopes of preventing such damage. This ranges from mechanical manipulation of the esophagus to esophageal cooling with various mechanisms including ice water lavage. This also includes the development of a cooled intraesophageal balloon with mixed results (Berjano EJ, 2005) (Lequerica JL B. E., 2008) (Lequerica JL B. E., 2008) (Tsuchiya T, 2007) ]. Further in-vitro evaluation of animals has been performed using a controlled saline circulating system (EPSac) which spares the esophagus from collateral thermal injury (Arruda MS, 2009). The novel idea of cooling the esophagus to prevent transmural damage has been documented as overwhelmingly positive. The most notable clinical evaluation of an esophageal cooling mechanism was performed by Tsuchiya et. which included a cooled water-irrigated intraesophageal balloon. (Tsuchiya T, 2007) A limitation of this study included the inability to assess the deeper muscular layer of the esophagus for evidence of injury. Several limitations to the above mentioned approaches include cost, physician availability, displacement of the esophagus, and ability to monitor the luminal esophageal temperature (LET).

## 2.2. Rationale

Left atrial ablation is a standard therapy in the management of atrial fibrillation; however esophageal injury is a known potential consequence of this procedure.[1-4] Delivery of the radiofrequency energy necessary to perform left atrial ablation has the potential to cause injury to the nearby esophagus and its associated vagal innervation, with injuries including ulceration, hematoma, spasm, disorders of esophageal motility, and atrial-esophageal fistula (the latter representing the extreme consequence of esophageal thermal injury due to posterior left atrial ablation).[1, 2] Esophageal mucosal lesions are commonly reported with an incidence ranging widely from 3% to 60%, and recent observations suggest a potential contribution of the transesophageal echocardiogram probe to esophageal injury seen after catheter ablation.[5] Although ablation of the left atrium poses the greatest risk, right atrial ablation also has the potential to allow esophageal damage to occur.

Although luminal esophageal temperature monitoring is one proposed measure to reduce the incidence of esophageal injury during atrial fibrillation ablation, the success of temperature monitoring has varied widely.[6, 7] It is fairly well established that effective measuring of the esophageal temperature depends on the position of the temperature probe relative to the heated cardiac tissue and also on good contact with the esophageal mucosa.[8] However, the esophagus often is mobile and shifts sideways by >2 cm in a patients undergoing catheter ablation for atrial fibrillation under conscious sedation.[9] Using fairly sophisticated approaches (e.g., deploying an ablation catheter with thermistor tip into the esophagus [as both a measurement device and a deflection tool], along with position confirmation using intracardiac echo) appears to be the only measurement technique that offers adequate protection.[6] This approach does not seem to be a technique that is routinely feasible (due to both the cost of equipment and the need for additional operators during the procedure).[6]

Moreover, there is the suggestion that the temperature probe used for esophageal temperature monitoring may contribute to a thermal effect and enhance direct tissue heating.[10]

Data from animal models show that the muscular layer is disrupted and necrotic myocytes are seen at the border of lesions in the esophagus even when no lesions on the epithelial layer were found, suggesting that cooling the deep muscular layer of the esophagus may be needed to prevent esophageal injury.[11] Prevention of esophageal injury via cooling of the esophagus has been investigated with mathematical modeling, preclinical models, and in the clinical arena. A finite element model in three dimensions investigating the effects of a cooled intra-esophageal balloon suggested that this approach could be a viable method to prevent thermal injury to the esophagus during intraoperative ablation of the left atrium.[12] Specifically, the authors found that (i) chilling the esophagus by means of a cooled balloon placed in the lumen minimizes the lesion in the esophageal wall compared to the cases in which no balloon is used (a collapsed esophagus) and with a non-cooled balloon; (ii) the temperature of the cooling fluid has a more significant effect on the minimization of the lesion than the rate of cooling (the thermal transfer coefficient for forced convection); and (iii) pre-cooling periods previous to RF ablation do not represent a significant improvement. Finally, the authors also suggest that the use of a cooled balloon could affect the transmural region of the atrial lesion, especially in the cases where the atrium is of considerable thickness (or in other words, in the presence of an atrium of considerable thickness, when a short duration and a low target temperature are programmed, the use of a cooled balloon could reduce the possibilities of achieving a transmural lesion in the atrium.

Subsequent study using an agar phantom-based model that was built to provide temperature readings at points between the esophageal lumen and the myocardium found that this method was able to provide effective thermal protection, although it was noted that the method could fail under certain unfavorable topical and procedural conditions.[13] In this study, a balloon utilizing water temperature of 5° C flowing at a rate of 25 mL per minute was used, which likely significantly limits the capability of this device to extract heat effectively.

Further study by this same group utilized varying coolant temperatures between 5°C and 37°C but maintained the coolant flow rate at 25 mL per minute.[14] The authors conclude that their results suggest that it is possible to thermally protect the esophagus (including the transmural region 2 mm away from the mucosal surface) during radiofrequency cardiac ablation by means of a cooling balloon placed in the esophageal lumen utilizing coolant temperature of 5°C or less and involving a precooling period of two minutes.

A custom developed system utilizing temperature controlled saline or water circulating at a flow rate between 50 to 300 mL per minute and a temperature of 5 to 25°C was evaluated using an in vitro Lamb heart – esophagus preparation, followed by an in vivo model with six dogs.[15] This custom system consisted of a 12 French probe with a distal expandable compliant latex sack with a diameter of up to 3 cm fully expanded. The authors found that a circulating water temperature of 25° C failed to spare the esophagus from thermal injury. However lowering the circulating temperature to 10° C or 5°C spared thermal injury (although expanding the balloon diameter by increasing circulating volume substantially to

intentionally displace the esophagus towards the left atrium allowed the development of shallow esophageal injury to the external layers of the muscularis).

A clinical study [16] of eight patients used a closed loop system with low flow rates (25 mL/min) and a water temperature of  $4.5 \pm 3.1^\circ\text{C}$  to build upon computer modelling demonstrating that a cooled balloon catheter (with a diameter of 10 mm) could transmurally cool the esophagus. They found that without cooling, esophageal temperature increased from a baseline of  $36.4^\circ\text{C}$  up to  $40.5^\circ\text{C}$  in under 30 seconds during ablation, whereas with the esophageal cooling balloon, esophageal temperature decreased down to  $30.2^\circ\text{C}$  with the balloon in place, and allowed an increase in temperature to only  $33.5^\circ\text{C}$ . The authors conclude that luminal esophageal temperature during the left atrial ablation was lowered by esophageal cooling using their catheter to a level where no thermal damage to the esophagus would likely be induced.

A study presented in 2007 in abstract form described the use of a saline filled esophageal balloon to attempt esophageal protection in an animal model, and found that in four dogs, a saline solution of  $10^\circ\text{C}$  was not sufficient to prevent thermal injury.[17] However, details of balloon configuration and, more importantly, coolant flow rate, were not provided, and a formal manuscript further describing these findings appears not to have yet been submitted.

Free water instillation into the esophagus has been tried with varying success. A study of 100 patients used very small volumes (5 mL) of ice water as the instilled volume, which was injected prior to RF energy delivery, and subsequently when esophageal temperatures reached  $42^\circ\text{C}$ . [18] The authors found that this approach alleviated the severity of esophageal lesions, but did not reduce the incidence: lesions occurred in 20% of the experimental group, and 22% of the controls, with three moderate and seven mild in the cooled group and three severe, one moderate, and seven mild in the control.

Another study utilized infusion of cooled saline mixed with Gastrografin or Iopamidol, with slightly higher, but still limited volumes (10 – 20 mL in repeated injected aliquots with a temperature of approximately  $10^\circ\text{C}$ ). [19] A total of 318 patients were randomized between groups receiving only temperature monitoring without cooling, temperature monitoring with cooling when temperature exceeded  $43^\circ\text{C}$ , and temperature monitoring with cooling received when temperatures exceeded  $39^\circ\text{C}$ . The percentage of patients free from any ulceration or erosion in each group was found to be 63.6%, 87.5%, and 95.2%, respectively, and the authors conclude that these findings suggest that esophageal damage can be reduced by reducing cooling solution into the esophagus via a gastric tube when luminal temperature exceeds  $39^\circ\text{C}$  during ablation.

In summary, although abundant data suggest that cooling of the esophagus during ablation procedures can protect against esophageal injury, no commercially available device has yet been shown to perform this task.

Our intention is to evaluate the use of an esophageal cooling catheter to protect the esophagus during atrial fibrillation RF ablation. This will theoretically eliminate esophageal tissue damage. As noted above, this is not a novel idea, however, there are several advantages that this device offers. The most significant of which includes a large area of

distribution of cooling effect throughout the length of the catheter as well as a large lumen. The lumen size provides more rapid thermal energy exchange thus limiting the extent of esophageal damage. There are no metal parts included in this catheter, therefore, eliminating the concern for the device acting as a wick for energy transfer and enhanced direct tissue heating. (Deneke T, 2011) The cooling catheter does not require advanced training for placement or monitoring and also acts as an oral-gastric tube during the procedure. This device is also cost effective as the cooling source is used by hospitals (nearly ubiquitously) for standard cooling blankets.

